## 9.16 End of Treatment Visit

A list of evaluations to be performed for the EOTV is provided in [Appendix 1](#). The EOTV should be performed after the participant has met study treatment discontinuation criteria specified in [Section 5.4](#); the visit should be performed within 30 days following the last dose of study drug. It is recognized that certain participants (such as those experiencing progression of disease) may be cared for in facilities other than the participating study site, may proceed to receive other cancer therapy, and/or may elect not to return to the study site. Therefore, this visit is considered optional, but should be carried out whenever possible. All required procedures and tests should be performed if the visit is performed. Note: the tumor assessment will not be performed at the EOTV for participants who had a previous scan performed < 28 days of the EOTV.

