## 14.2 Analysis Populations

The study analyses will be performed on the following populations:

- Safety Population: All participants who received at least one dose of study drug. This population will be used for analyses of safety, pharmacodynamics, and immunogenicity. It will also be used for summary of baseline data and analyses of PFS, rPFS, and OS.
- Response Evaluable Population: All participants who received at least one dose of study drug, had baseline measurable or non-measurable disease, and had at least one post-baseline radiographic tumor assessment or discontinued treatment due to clinical progressive disease or death. This population will be used for summary of tumor assessment data and analyses of response rates.
- PSA Response Evaluable Population: mCRPC participants with a baseline PSA  $\geq 2$  ng/mL and at least 1 post baseline PSA measurement. This population will be used to calculate and summarize PSA response rates.

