|                                                         | PSA measurements to be performed at baseline and then repeated predose on Day 1 of each cycle, approximately 30 days after the last study treatment administration (EOTV), and every 12 weeks (± 7 days) during the follow-up period until disease progression, start of another cancer therapy, or the study cutoff date, whichever comes first. |         |              |                |        |                 |                                |                                              |                 |                                 |                 |                                             |                    |
| Pharmacokinetics                                 | See Appendix 3                                                                                                                                                                                                                                                                                                                    |         |              |                |        |                 |                                |                                              |                 |                                 |                 |                                             |                    |
| Serum Cytokines                                  | See Appendix 3                                                                                                                                                                                                                                                                                                                    |         |              |                |        |                 |                                |                                              |                 |                                 |                 |                                             |                    |

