4 ANALYSIS POPULATIONS

4.1 Analysis Populations

The study analyses will be performed on the following populations:

- Safety Population: All participants who received at least one dose of any study drug. This population will be used for analyses of safety, pharmacodynamics, and immunogenicity. It will also be used for summary of baseline data and analyses of PFS, rPFS, and OS.
- Response Evaluable Population: All participants who received at least one dose of any study drug, had baseline measurable disease, and had at least one post-baseline radiographic tumor assessment or discontinued treatment due to clinical progressive disease or death. This population will be used for summary of tumor assessment data and analyses of response rates.
- PSA Response Evaluable Population: mCRPC participants with a baseline PSA \geq 2 ng/ML and at least 1 post-baseline PSA measurement. This population will be used to calculate and summarize the PSA response rates.

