6.7.5 Analyses of Metastatic Castration-resistant Prostate Carcinoma-specific Endpoints

- rPFS: The censoring rules in [Table 2](#) will be applied to rPFS analysis. The analysis of rPFS will be the same as that described for PFS.
- PSA:

PSA response rate will be calculated for participants with a baseline PSA ≥ 2 ng/mL and at least 1 post-baseline value (i.e. PSA response evaluable population). The PSA response rate will be summarized at 12 weeks from baseline. The 2-sided 95% exact binomial CI of the response rate will be calculated.

The percent change in PSA from baseline overall time will be summarized by visit and presented individually by spider plot. The percentage of change in PSA from baseline to 12 weeks (or earlier if treatment is discontinued), and the best PSA percent change from baseline will be presented by waterfall plots.

The Kaplan-Meier method will be applied to estimate time to PSA progression in the PSA response evaluable population. PSA measurements are performed at baseline and then repeated prior to each dose of each treatment visit, approximately 30 days after the last study treatment administration (EOTV), and every 12 weeks (± 7 days) during the follow-up period until disease progression, start of another cancer therapy, or the study cutoff date, whichever comes first.

Participants without PSA progression at the time of analysis will be censored to the date of their last PSA assessment. The last three rules in **Table 2** will be applied to PSA progression analysis, with the changes from “progression” and “tumor assessment” to “PSA progression” and “PSA assessment”, respectively.

- SSE: SSE rate will be summarized. Specifically, SSE rate per 100 patient-year will be calculated as the number of each of the SSEs, including the occurrence of new symptomatic pathological fracture, use of external beam radiation to relieve bone pain, spinal cord compression, or tumor-related orthopedic surgical intervention, divided by the total patient-years in the mCRPC cohort. The Kaplan-Meier method will be applied to estimate time to SSE. Participants without SSE at the time of analysis will be censored at the last assessment. For each participant, the eCRF documenting any SSEs is scheduled to be completed pre-dose of each treatment. Participants without any SSE assessment will be excluded for the SSE endpoint analysis.

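### The PSA response rate leaves out mCRPC participants who die or stop for clinical progression before any post-baseline PSA, so it can only err upward, and ORR treats such participants differently

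*SAP*

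**What the plan says.** The secondary objectives in both documents include describing the PSA response rate in mCRPC. SAP 5.1.4 defines response as a fall of at least 50% from baseline, confirmed at least 3 weeks later.

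The denominator is given in four places, and all four agree:

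- SAP 4.1 requires baseline PSA ≥ 2 ng/mL and "at least 1 post-baseline PSA measurement. This population will be used to calculate and summarize the PSA response rates".
- SAP 6.7.5 repeats this with "at least 1 post-baseline value (i.e. PSA response evaluable population".
- Protocol 14.2 requires "at least 1 post baseline PSA measurement. This population will be used to calculate and summarize PSA response rates".
- Protocol 14.6.4.2 restates the condition.

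None of them provides for death or clinical progression before the first post-baseline PSA. Neither document plans an all-treated or sensitivity analysis of PSA response.

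SAP 4.1 also defines the Response Evaluable Population used for ORR. A participant enters it who "had at least one post-baseline radiographic tumor assessment or discontinued treatment due to clinical progressive disease or death". Early failure without a scan therefore stays in the ORR denominator as non-response. The baseline condition differs between documents: the SAP says "had baseline measurable disease" and Protocol 14.2 says "had baseline measurable or non-measurable disease".

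**The concern.** A participant with no post-baseline PSA cannot meet the response definition, so the exclusion takes out non-responders and never a responder. When the reason for the missing value is death or clinical progression, the exclusion is tied to outcome. The reported figure then describes response among those who remained long enough to be measured, not among treated mCRPC participants.

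The boundary is also hard to defend as an evaluability rule. A participant with exactly one post-baseline PSA cannot have a confirmed response either, yet stays in the denominator as a non-responder. In the Module A expansion, death just before the Day 22 draw removes a participant, while death just after it counts as failure.

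These cohorts exist to provide preliminary estimates, so what is at stake is how the estimate reads. A one-way error is not repaired by a wide confidence interval. The post-baseline clause also does nearly all the excluding, because PSA of at least 2 ng/mL is already an entry criterion for the mCRPC expansion cohorts (Protocol 5.1).

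**Working it through.** **Inputs.** Cohort size N = 16, with 24 more mCRPC participants possible, so 16 + 24 = 40 (SAP 3.2). The interval is the two-sided 95% exact binomial (SAP 6.7.5). The number m of treated participants with baseline PSA ≥ 2 ng/mL and no post-baseline PSA is not given in either document; m = 1 to 4 is assumed to show a range. The responder counts r are also illustrative.

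**The plan's own figures.** Clopper-Pearson intervals reproduce all six rows of SAP Table 1 (the same as Protocol Table 10), for example 4/16 = 25.0% (7.3, 52.4) and 5/16 = 31.3% (11.0, 58.7).

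**Formula.** None of the m participants can be a responder, so r is the same under both denominators:

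- all treated: r/N
- as planned: r/(N−m)
- ratio: [r/(N−m)] / [r/N] = N/(N−m)

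The ratio is never below 1. It equals 1 when m = 0. When r = 0 both rates are 0.

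**N = 16, r = 4**

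| m | Planned rate (95% CI) | N/(N−m) | Shift, points |
|---|---|---|---|
| 0 | 4/16 = 25.0% (7.3, 52.4) | 1 | 0 |
| 1 | 4/15 = 26.7% (7.8, 55.1) | 1.07 | +1.7 |
| 2 | 4/14 = 28.6% (8.4, 58.1) | 1.14 | +3.6 |
| 3 | 4/13 = 30.8% (9.1, 61.4) | 1.23 | +5.8 |
| 4 | 4/12 = 33.3% (9.9, 65.1) | 1.33 | +8.3 |

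**N = 16, r = 5, m = 2.** 5/16 = 31.3% (11.0, 58.7) becomes 5/14 = 35.7% (12.8, 64.9).

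**N = 40, r = 16.** 40.0% (24.9, 56.7) becomes 41.0%, 42.1%, 43.2% and 44.4% for m = 1 to 4, with factors 1.03, 1.05, 1.08 and 1.11.

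**Can m exceed zero?** In the Module A expansion, PSA is drawn before each dose, so the first post-baseline value is due at Day 22 (Protocol Appendix 1). A further draw is due about 30 days after the last dose, at the end-of-treatment visit, but Protocol 9.16 says "this visit is considered optional, but should be carried out whenever possible" and recognises that participants with progression may not return. Follow-up PSA about every 12 weeks stops at progression or new therapy (Protocol 9.8, 9.17). Early death, and clinical progression with no return visit, can therefore leave no post-baseline PSA.

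**Same early death, other endpoints.** For ORR it is a non-response, if the baseline disease condition is met. For rPFS, analysed in the Safety Population, it is an event (SAP 5.1.4 and Table 2). For PSA response the participant is absent.

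**The case against.** The strongest reply is that little turns on this. The design is estimation only, and no test or threshold uses the PSA response rate. The mCRPC expansion is sized mainly on the 6-month rPFS rate, where early deaths do count. With 5/16 the interval is already 58.7 − 11.0 = 47.7 points wide, against a shift of about 4.5 points at m = 2. Disposition tables will list reasons for stopping treatment (SAP 6.3.1). All of this is true and limits the importance. It does not change the direction of the error, and disposition tables will not show who was left out of the PSA denominator.

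The conflict with ORR is also narrower than it first looks. The Response Evaluable Population rescues only death and clinical progression; participants without a scan who stop for toxicity or withdraw are dropped there too. Under the SAP wording it covers only measurable disease, while mCRPC without measurable disease may enrol (Protocol 5.1). An all-treated PSA denominator therefore goes further than consistency with ORR requires, and is partly a choice of estimand.

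A reader might also infer several stronger points that the documents do not support:

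- *Toxicity stops are lost in the same way.* Follow-up PSA about every 12 weeks can bring them back into the population.
- *Inflation is larger in Module B, distorting a comparison of modules.* Appendix 1 for Module B has "PSA measurements to be performed at baseline and then repeated predose on Day 1 of each cycle", which puts the first draw at about Day 43, but SAP 6.7.5 describes PSA before each dose with no Module B exception. No between-module comparison is planned (Protocol 14).
- *Time to PSA progression is biased by the same exclusion.* Death is not an event there, and a participant with no post-baseline PSA would be censored at the start and add nothing to the Kaplan-Meier estimate.
- *An early-death rate can be read from the 24-week life-expectancy criterion.* That is an eligibility floor, not a median survival.

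**Conclusion.** The point holds as a cheap improvement to a secondary endpoint. The rule can only overstate the PSA response rate, by a factor N/(N−m). For a cohort of 16 that is 1.07 to 1.33 for m = 1 to 4; for 40 it is 1.03 to 1.11.

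It would be going too far to say that the rate is overstated. That requires at least one excluded participant and at least one responder, and the documents give no early-loss rate. In the Module A expansion, with a first draw at Day 22, m is probably small. The values of m and r above are assumptions; the direction of the error follows from the response definition alone.

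The inconsistency with ORR is real for participants who stop for clinical progression or die, and under the SAP wording only for those with measurable disease.

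**What to change.** In SAP 4.1 and 6.7.5 and Protocol 14.2 and 14.6.4.2, define the PSA response denominator as all mCRPC participants who received at least one dose and had baseline PSA ≥ 2 ng/mL, and count those with no post-baseline PSA as non-responders. At minimum, add the clause for clinical progression or death already used in the Response Evaluable Population.

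Keep the present population as a supportive analysis, and report how many treated participants it excludes and why.

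The cost is a short wording change in each document and no new data. The downside is a reported rate that may be slightly lower.

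Separately, reconcile the PSA schedule in SAP 6.7.5 (before each dose) with Protocol Appendix 1 for Module B (Day 1 of each cycle).

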5 ENDPOINTS

5.1 Efficacy Endpoints

5.1.1 Response Endpoints

Response by RECIST v1.1: The best overall response (BOR) will be categorized as complete response (CR), partial response (PR), stable disease (SD), progressive disease (PD), or not evaluable (NE). To be qualified as BOR, CR and PR require confirmation at least 4 weeks after initial observation of such response, and SD requires to be observed at least once after 6 weeks from the start of MGC018 treatment for Module A or MGC018 and MGA012 combination treatment for Module B.

5.1.2 Time-to-event Endpoints

- PFS: PFS is defined as the time from the first dose date of MGC018 treatment (Module A) or MGC018 and MGA012 combination treatment (Module B) to the date of first documented progression or death from any cause, whichever occurs first. The documented progression is determined by radiographic assessment using RECIST v1.1. PFS will be calculated as:

$$\text{PFS (months)} = (\text{date of event [documented progression or death] or date of censoring} - \text{first dose date} + 1) / (365.25/12)$$

- Duration of response (DoR): DoR is defined as the time from the date of initial response (CR or PR) to the date of first documented progression or death from any cause, whichever occurs first. DoR is calculated only for the responders (i.e., participants who have CR or PR). The documented progression is determined by radiographic assessment using RECIST v1.1. DoR will be calculated as:

$$\text{DoR (months)} = (\text{date of event [documented progression or death] or date of censoring} - \text{date of initial response} + 1) / (365.25/12)$$

- OS: OS is defined as the time from the first dose date of MGC018 treatment for Module A or MGC018 and MGA012 combination treatment for Module B to the date of death from any cause. OS will be calculated as:

$$\text{OS (months)} = (\text{date of death or last known alive} - \text{first dose date} + 1) / (365.25/12)$$

5.1.3 Tumor Size Change Over Time Endpoints

The tumor size is defined as the sum of diameters of the target lesions. Tumor size change over time from baseline will be calculated.

PRO will be assessed using the Brief Pain Inventory-short form (BPI-sf). The BPI-sf is an exploratory 9 item self-administered written questionnaire used to evaluate the severity of a participant's pain and the impact of the pain on daily functioning.

5.2 Safety Endpoints

5.2.1 Adverse Events

Safety will primarily be addressed by evaluations of adverse events (AEs). An AE is defined as any untoward medical occurrence in a participant or clinical trial participant associated with the use of a drug in humans, whether or not considered drug related. An adverse event can therefore be any unfavorable and unintended sign (including an abnormal laboratory finding, for example), symptom, or disease temporally associated with the use of a medicinal product, whether or not considered related to the medicinal product. Only TEAEs will be summarized as safety endpoints. A TEAE is defined as any event that is newly occurring on or after the administration of study drug or an event that existed before but increased in severity on or after study drug administration.

All adverse events whether serious or non-serious, will be reported from the time a signed and dated informed consent form (ICF) is obtained through 30 days following the last dose of study drug or until the start of a subsequent systemic anticancer therapy (whichever occurs first). These events will be recorded by the Investigators in the eCRFs. AEs will be coded using the most recent version of the Medical Dictionary for Regulatory Activities (MedDRA). An assessment of severity grade will be made using NCI-CTCAE Version 4.03.

Both protocol-related AEs and serious adverse events (SAEs) will be collected from the time the participant has consented to study participation. AEs and SAEs reported between the time the participant signs the ICF and the administration of the first dose of study drug will be captured as concurrent medical history unless the events are attributed to protocol-specified procedures. Events attributed to protocol-specified procedures will be collected on the Adverse Event eCRFs and SAE Report form as appropriate. After 30 days following the last dose of study drug administration, if an investigator becomes aware of an SAE that s/he suspects is related to study drug, the investigator should report the event to the sponsor.

5.2.2 Laboratory Evaluations

Standard safety laboratory parameters collected via a local laboratory will be summarized and graded according to CTCAE Version 4.03.

5.2.3 Physical Examinations

Physical examinations including weight and height will be performed according to the schedules outlined in the latest version of the protocol.

5.2.4 Vital Signs and Performance Status

Vital signs include temperature, pulse, blood pressure, and respiratory rate. Vital signs and Eastern Cooperative Oncology Group (ECOG) performance status will be performed according to the schedules outlined in the latest version of the protocol.

5.2.5 Electrocardiograms

All electrocardiograms (ECGs) should be obtained in triplicate (3 ECGs per time point at approximately 1-minute intervals) according to the schedules outlined in the latest version of the protocol in order to evaluate the potential cardiac effects of study drug, including QTc interval prolongation. Central interpretation of ECGs will be used for data analysis purposes.

5.2.6 Echocardiography/MUGA scan

An echocardiogram or multigated acquisition (MUGA) scan to evaluate left ventricular ejection fraction (LVEF) will be performed according to the schedules outlined in the latest version of the protocol.

5.3 Pharmacokinetic, Pharmacodynamic, and Immunological Endpoints

PK samples, ADA samples, and pharmacodynamic biomarker specimens will be collected according to the schedules outlined in the latest version of the protocol.

6 STATISTICAL METHODOLOGY

6.1 General Considerations

Safety and efficacy summaries will be provided for each dose level cohort during dose escalation and for all dose level cohorts combined, as well as for expansion cohorts where appropriate. Response rates will be calculated for the response evaluable population.

Unless otherwise specified, the following general considerations are applied in data analyses:

- The baseline value is defined as the latest value on or prior to the first dose of study treatment.
- Categorical data will be summarized by the number and percent of participants falling within each category.
- Continuous variables will be summarized by descriptive statistics, including mean, standard deviation, median, minimum, and maximum.
- Time-to-event endpoints will be summarized by the number and percent of the event, median time and corresponding 95% confidence interval (CI), and event free rate and corresponding 95% CI at the specified time points of interest.
- The impact of COVID-19 may be assessed and analyzed on a case-by-case basis. In particular, the following analyses may be performed if there are enough COVID-19 positive participants to render the analyses meaningful:
 - Number of participants discontinued study treatment and/or discontinued from study due to COVID-19, if such a reason is collected
 - Summary of tumor response, PFS, rPFS and OS
 - Summary of study drug interruption, delay or withdrawal due to COVID-19, if such a reason is collected
 - Listing of protocol deviations due to COVID-19
- All data summaries and tabulations will be conducted using SAS® software Version 9.4 or higher.

6.2 Missing Data

Data that are reported as missing will be treated as missing in all data summaries. Imputation rules for partially recorded dates, in case that the complete dates are required to carry out an analysis, will be provided in the Statistical Programming Plan (SPP). In descriptive summaries for safety, observations that are spurious (extreme relative to the majority of the data) will not be altered or removed from the summary.

6.3 Participant Disposition and Baseline Characteristics

6.3.1 Participant Disposition

For participant disposition, the number and percentage of participants who reach various study milestones are summarized: All screened participants are broken down by screen failures (with reasons if collected) and enrolled. Then the category of enrolled is broken down by never treated (with reasons if collected) and treated. The category of treated will further be broken down by treatment ongoing and treatment discontinuation (with reasons for discontinuation, which also include protocol-defined treatment completion, if any). The end of study status for all enrolled participants will also be included. Duration of follow-up since first dose of study treatment, defined as from the date of first dose of MGC018 treatment (Module A) or MGC018 and MGA012 combination treatment (Module B) to the date of withdraw of consent, lost to follow up, death, or the last contact date, will be summarized.

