### **5.3 Withdrawal of Participant from the Study**

Participants who withdraw before Study Day 21 (Module A) or Study Day 42 (Module B) during the Dose Escalation Phase for a reason unrelated to drug toxicity may be considered to have inadequate data to support dose escalation. In this case, replacement participants may be enrolled in the same dose level. These participants will be followed for safety assessments (see [Section 12.2](#)).

A participant may be determined to be LTFU after there have been at least 3 documented phone or electronic contact attempts. If this fails, a certified letter should be sent to the participant. Only after these attempts have failed can a participant be determined to be LTFU.

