For both the Dose Escalation Phase of Module A and Module B and the Cohort Expansion Phase of Module B, tumor assessments will occur at Day 42 of each cycle, for the first 4 cycles, and every other cycle thereafter. For the Cohort Expansion Phase of Module A, the tumor assessments will occur every 9 weeks (63 days). For Module A, the DLT evaluation period will be 21 days in duration; for Module B, the DLT evaluation period will be 42 days in duration. Participants who complete a given cycle, remain clinically stable, do not experience a DLT or other unacceptable toxicity, and do not otherwise meet the criteria for permanent treatment discontinuation may be eligible for additional treatment with MGC018 alone or in combination with MGA012 for up to a total of 18 cycles (approximately 2 years).

Following the last dose of study drug, all participants in Module A and Module B Cohort Expansion Phases will be followed every 3 months (90 days) for survival during a 2-year Survival Follow-up Period, until criteria are met for study discontinuation. Participants in Module A Dose Escalation Phase will be followed similarly for survival status until approval of Amendment 3, at which point they will be discontinued from follow up.

Figure 1

[figure not shown]
[figure not shown]
Overall Study Design

Note: MTD-2 = the dose level that is 2 dose levels below the MTD defined for MGC018 monotherapy.

MTD-1 = the dose level that is 1 dose level below the MTD defined for MGC018 monotherapy.

Abbreviations: mCRPC = metastatic castrate-resistant prostate carcinoma; MTD = maximum tolerated dose; NSCLC = non-small cell lung cancer; Q3W = every 3 weeks; RP2D = recommended phase II dose; SCCHN = squamous cell carcinoma of the head and neck; TBD = to be determined; TNBC = triple negative breast cancer.

Figure 2**MGC018 Monotherapy Dosing Schedule (Module A)****Figure 3****MGC018 and MGA012 Combination Dosing Schedule (Module B)**

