6.7.2 Analyses of Time-to-event Endpoints

6.7.2.1 Analyses of Progression-free Survival

The Kaplan-Meier method will be applied to estimate PFS curve, median PFS, and PFS rates at 3 and 6 months. The method of Brookmeyer and Crowley (1) will be used to construct 95% CI for median PFS. The 95% CIs for PFS rate will be calculated by normal approximation after log(-log) transformation.

For patients who are not known to be dead or progressed at the time of data cut-off for PFS analysis, the PFS will be censored at the date of the last tumor assessment. For primary PFS analysis, Table 2 describes the censoring rules.

Table 2 Censoring Rules for Primary Progression-free Survival Analysis

Situation	Date	Outcome
No baseline tumor assessments	First dose date	Censored
Death prior to first scheduled tumor assessment	Date of death	Progressed
No post-baseline tumor assessments in absence of death prior to first scheduled tumor assessment	First dose date	Censored
Documented progression	Date of progression	Progressed
Initiation of alternative anti-cancer treatments in absence of documented progression	Date of last tumor assessment prior to initiation of such treatment	Censored
Death or documented progression immediately after missing two or more consecutive scheduled tumor assessments	Date of last tumor assessment prior to missed assessments	Censored

PFS will be analyzed by tumor type when sample size warrants. A sensitivity analysis for PFS may be performed to assess the robustness of above primary PFS analysis. For this sensitivity analysis, the censoring rules are the same as in **Table 2** except that the documented progression or death will be considered as an event, regardless when it occurs during the study.

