6.7.2.3 Analyses of Overall Survival

The Kaplan-Meier method will be applied to estimate OS curve, median OS, and OS rates at 6 and 12 months. For patients who are not known to be dead at the time of data cut-off for OS analysis, the OS will be censored at the time they are last known to be alive. The method of Brookmeyer and Crowley ([1](#)) will be used to construct 95% CI for median OS. The 95% CIs for OS rate at 6 and 12 months will be calculated by normal approximation after log(-log) transformation. OS will be analyzed by tumor type when sample size warrants.

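### SAP 6.3.1 ends duration of follow-up at death, so its median reflects survival as well as length of observation; a reverse Kaplan-Meier follow-up should be added

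*SAP*

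**What the plan says.** SAP 6.3.1 (Participant Disposition) starts duration of follow-up at the first dose of MGC018 (Module A) or of the combination (Module B) and runs it "to the date of withdraw of consent, lost to follow up, death, or the last contact date, will be summarized". It names no estimation method, so the general rule in SAP 6.1 applies: "Continuous variables will be summarized by descriptive statistics, including mean, standard deviation, median, minimum, and maximum".

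The related definitions are:

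- OS start, SAP 5.1.2: "OS is defined as the time from the first dose date of MGC018 treatment for Module A", and correspondingly from the combination in Module B.
- OS censoring, SAP 6.7.2.3: "the OS will be censored at the time they are last known to be alive".
- PFS censoring, SAP 6.7.2.1: "the PFS will be censored at the date of the last tumor assessment". SAP 6.7.5 applies the same censoring table to rPFS.
- Planned observation of the expansion cohorts, SAP 3.1: participants "will be followed every 3 months (90 days) for survival during a 2-year Survival Follow-up Period".

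Neither document names a reverse Kaplan-Meier or potential follow-up measure, or a follow-up time that ends at the last tumor assessment.

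**The concern.** The follow-up measure and OS start on the same date. Both end at death for those who die, and at essentially the same date for those who do not. Each participant's follow-up is therefore essentially the observed OS time with the death indicator dropped. Its median mixes two things: how long participants lived and how long they could have been watched.

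Readers commonly use median follow-up to judge whether landmark rates rest on enough observation. The SAP plans PFS and rPFS rates at 3 and 6 months and OS rates at 6 and 12 months, and SAP 3.2 bases the mCRPC expansion on the 6-month rPFS rate. With the SAP measure, a cohort with worse survival looks less followed than one with better survival cut on the same day. A 12-month OS rate could also appear beside a median follow-up of 9 months when the cohort was under observation for a median of 18.

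For PFS and rPFS there is a second mismatch. The measure runs to death or last contact, while those endpoints are censored at the last scan. Protocol 9.17 makes collection of progression data after treatment optional, so contact can continue well after scanning has stopped.

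**Working it through.** The documents state no follow-up figure, so there is none to reproduce. The check asks what the SAP measure would report under plausible conditions.

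**Inputs from the documents**
- Expansion accrual about 12 months (Protocol 4.5).
- Cohorts of up to 16; the mCRPC cohort may gain 24 (SAP 3.2), hence 16 + 24 = 40.
- Median OS 7-9 months in second-line NSCLC (Protocol 2.2.3). Fewer than 20% alive at 2 years in recurrent SCCHN (Protocol 2.2.1).

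**Assumptions**
- Exponential survival with median *m* of 7, 9 or 12 months, uniform accrual, and no dropout.
- Data cut *f* = 6, 12 or 24 months after the last participant starts, which is month 18, 24 or 36 after the first.

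**Formula.** Let T be survival time and C potential follow-up, uniform from *f* to *f* + 12. The SAP measure is X = min(T, C), so

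P(X > x) = 2^(-x/m) × P(C > x).

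For x up to *f*, P(C > x) = 1. So whenever *m* is at most *f*, the median of X is exactly *m*, whatever *f* is. Median potential follow-up is *f* + 6, that is 12, 18 or 30 months.

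When *m* exceeds *f*, the median solves 2^(-x/m) × (f + 12 - x)/12 = 0.5:
- *m* = 9, *f* = 6: at x = 7.4, 0.566 × 10.6/12 = 0.50.
- *m* = 12, *f* = 6: at x = 8.3, 0.619 × 9.7/12 = 0.50.

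In both cases the answer is below *m* and below the potential follow-up of 12 months.

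**Simulation, n = 16, 4,000 runs per row.** Entries in months are medians over runs; reverse Kaplan-Meier entries are over runs where it could be estimated. The last column is the share of runs in which the SAP median and the Kaplan-Meier median OS were identical.

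| m | f | Dead | SAP median | KM median OS | Reverse KM | Identical |
|---|---|---|---|---|---|---|
| 7 | 6 | 68% | 6.5 | 6.9 | 11.9 | 43% |
| 7 | 12 | 82% | 7.0 | 7.0 | 18.0 | 96% |
| 7 | 24 | 95% | 7.0 | 7.0 | 29.1 | about 100% |
| 9 | 6 | 59% | 7.4 | 8.4 | 12.1 | 21% |
| 9 | 12 | 74% | 9.1 | 9.0 | 18.1 | 80% |
| 9 | 24 | 90% | 9.1 | 9.1 | 29.6 | about 100% |
| 12 | 6 | 49% | 8.4 | 10.3 | 12.0 | 7% |
| 12 | 12 | 64% | 11.7 | 11.7 | 18.1 | 51% |
| 12 | 24 | 82% | 12.0 | 11.9 | 30.0 | 98% |

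Cohorts of 40 show the same pattern.

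The governing condition in this model is whether *m* is at most *f*; the share of deaths is only a guide to it. With *m* = *f* = 24, for example, 58% have died and the large-sample SAP median still equals median OS at 24.0 months.

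**Can the alternative be estimated?** At n = 16 the reverse Kaplan-Meier median did not exist in 3% (*m* = 9) and 9% (*m* = 7) of runs at *f* = 12, and in 19% and 42% at *f* = 24. These shares count a curve that just reaches 0.5 as giving a median; requiring it to fall below 0.5 makes them higher. A finite upper 95% limit was missing in 92-99% of runs at *f* = 12 and in nearly all at *f* = 24.

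**The case against.** The strongest reply is that the SAP never gives this measure the task of showing maturity. It appears under disposition, and as a record of time actually observed it is correctly defined, because observation does end at death. SAP 6.1 also plans the number and percent of events, medians with 95% CIs and event-free rates with CIs, and SAP 6.3.1 itself reports end-of-study status. A reader of the full tables would not be misled about how many deaths had occurred. All of this stands, and it limits the point to reporting.

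The size of the effect also depends on assumed cut dates and an assumed survival shape. The documents fix neither, and the 7-9 month figure is for NSCLC, not for every cohort.

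Nor is the alternative free of cost. Reverse Kaplan-Meier rests on the few survivors, so it is weakest in the small, high-mortality cohorts where it is most wanted. Used alone with OS dates, it could make rPFS look better supported by scans than it is. These two objections shape the fix; they do not remove the need for it.

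**Conclusion.** The point holds as a low-severity reporting improvement. The SAP 6.3.1 median depends on survival as well as on observation time. When most of a cohort has died and the cut falls later than median survival, it approximates median OS: for median OS of 7-9 months at the two later cuts, the two were identical in 80% to about 100% of runs. In those rows the reverse Kaplan-Meier median was roughly 9 to 22 months longer (18.1 - 9.1 = 9.0; 29.1 - 7.0 = 22.1). These sizes rest on exponential survival, uniform 12-month accrual, no dropout and the assumed cuts.

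Three stronger readings are not supported:

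- *The figure always repeats median survival.* With 59% and 49% dead in the early-cut scenarios, the two agreed in only 21% and 7% of runs. The SAP figure then fell below both median OS and potential follow-up.
- *Participants lost to follow-up will have follow-up longer than their OS time.* Protocol 5.3 says that "Only after these attempts have failed can a participant be determined to be LTFU", which governs when the status may be assigned. It does not say which date is recorded, and the SAP leaves programming detail to the SPP.
- *Efficacy results are affected.* No estimate, interval, dose decision or sample-size figure uses this measure, and the primary objective is safety and the MTD or MAD.

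**What to change.** In SAP 6.3.1:

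1. Keep the current measure, but label it *observed time on study*.
2. Add, by cohort, reverse Kaplan-Meier median follow-up for OS with its 95% CI. Deaths are censored, and the event is the same last-known-alive date that censors OS in SAP 6.7.2.3.
3. Add the same for PFS, and for rPFS in mCRPC. Progression or death is censored, and the event is the last tumor assessment date.
4. Where the reverse Kaplan-Meier median or its CI cannot be estimated, report the median and range of potential follow-up from first dose to data cutoff.

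The cost is a few sentences and one or two extra Kaplan-Meier runs on data already collected. The drawback is imprecise or missing medians in 16-participant cohorts with few survivors, which item 4 covers.
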